## **10.0 Vulnerable Populations**

### *10.1 Vulnerable Populations:*

- Children
- Pregnant women/Fetuses/Neonates
- Prisoners
  - Adults lacking capacity to consent and/or adults with diminished capacity to consent, including, but not limited to, those with acute medical conditions, psychiatric disorders, neurologic disorders, developmental disorders, and behavioral disorders
  - Approached for participation in research during a stressful situation such as emergency room setting, childbirth (labor), etc.
  - Disadvantaged in the distribution of social goods and services such as income, housing, or healthcare
  - Serious health condition for which there are no satisfactory standard treatments

- Fear of negative consequences for not participating in the research (e.g. institutionalization, deportation, disclosure of stigmatizing behavior)
- Any other circumstance/dynamic that could increase vulnerability to coercion or exploitation that might influence consent to research or decision to continue in research
- Undervalued or disenfranchised social group
- Members of the military
- Non-English speakers
- Those unable to read (illiterate)
- Employees of the researcher
- Students of the researcher
- None of the above

*10.2 Additional Safeguards:*

**11.0 Local Number of Participants**

*11.1 Local Number of Participants to be Consented:* 40 patients consented with goal of 22 patients enrolled in the study

**12.0 Local Recruitment Methods**

*12.1 Recruitment Process:* No recruitment posters. Only recruit from surgical lists. Patients will be recruited from the group of adult surgical patients at the University of Minnesota undergoing shoulder surgery and receiving an interscalene block scheduled for overnight stay that elected to participate in another ISB bupivacaine versus LB shoulder study. Patients will be approached at the preoperative assessment clinic or surgeon's clinic at the Clinic and Surgery Center if possible by a research staff member to determine their interest in participation. If they decide to be a participant they will be consented and given a copy of their consent form for their records and a consent will be scanned and placed into EPIC. These patients will have significant time to review the study with research staff as well as the physicians performing the procedure due to the fact they arrive several hours prior to their scheduled surgery. All subjects will have enough time to ask questions about the study and the potential risks involved regardless of which venue they are consented.

*12.2 Identification of Potential Participants:* Patients will be identified by members of the treatment team in either the surgeon's clinic, pre-assessment clinic, or preoperative area. Patients who have opted out of research will not be asked to participate in the study. Patients will be approached to consent for the study by a surgeon, anesthesiologist, or member of the research team. Patients who agree to participate in the study will sign both a study

consent and HIPAA authorization allowing the use of specified information contained in medical records for research purposes.

12.3 Recruitment Materials: n/a

12.4 Payment: n/a

### **13.0 Withdrawal of Participants**

13.1 Withdrawal Circumstances: Subjects who have consented prior to the day of surgery and for some reason choose not to participate will be withdrawn and a notation will be made in the study records and these people will be considered screen failures. The surgeon may choose to withdraw the patient from the study prior to surgery for any medical reason or if they suffer a major life threatening adverse event.

13.2 Withdrawal Procedures: If the patient is withdrawn from study prior to the procedure, they will be noted in study records as screen failures. If they undergo the procedure and they decide they no longer want to be a part of the study or withdrawn by the physician, they will be withdrawn and no further data will be collected. This will also be noted in the study documentation.

13.3 Termination Procedures: If the study is terminated for any reason, or there is more than 5 % major adverse events the data that is already collected will be stored in a secure location only accessible to research personnel on this study. No further data will be collected if the study is terminated. Risks to Participants

13.4 Foreseeable Risks: There is a risk of loss of privacy as well as inconvenience the patient as we will ultrasound them prior to and after surgery. Otherwise this is a minimal risk study

13.5 Reproduction Risks: n/a

13.6 Risks to Others: n/a

### **14.0 Potential Benefits to Participants**

14.1 Potential Benefits: There are no potential benefits to the patient from this study.

### **15.0 Statistical Considerations**

15.1 Data Analysis Plan: We will use the average of the three US exams for each timed measurement as the definitive measurement. We will also use FEV1, FVC (or FEV6) and FEV1/FVC (or FEV6) ratio for each time period as a secondary measurement. This data will be given to the statistician who will compare those in the LB ISB group to the bupivacaine ISB group to evaluate for differences (if any) between the movement of the diaphragms in each group.

*15.2* Power Analysis: We assumed a 5% rate of block at 24 hours in bupivacaine and a 66% block for liposome bupivacaine. With an alpha of 0.05 and power of 80% we determined we need 9 patients in each group. Assuming we would have 20% patients drop out, screen fail, or discharge early we planned to enroll 11 per group for total of 22 patients.

*15.3* Statistical Analysis: This study will be analyzed by our staff biostatistician. The data will be de-identified and shared with him in box. The statistician will be provided the protocol so they are able to analyze for primary and secondary objectives.

*15.4* Data Integrity: All patients will be assigned a unique patient identifier. The data that will be sent to the statistician will be de-identified.

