## 2.0 Objectives

- 2.1 Purpose: To evaluate the movement of the diaphragm after an interscalene block with liposome bupivacaine (LB) compared to interscalene block (IB) with bupivacaine. **This study will evaluate if there is a possible prolonged phrenic nerve paralysis when using liposome bupivacaine in an interscalene block, using ultrasound.**

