## 3.0 Background

- 3.1 Significance of Research Question/Purpose: To date there is no previous study looking at diaphragm movement after an Liposomal Bupivacaine Interscalene Block. It is important to see how long the phrenic nerve is affected by this block if at all.
- 3.2 Preliminary Data: We have not routinely examined that patient's diaphragm via ultrasound after ISB at M Health. Patients have not been readmitted for breathing problems with our current practice.
- 3.3 Existing Literature: There is no previous literature in LB ISB. Urmev et al. showed 100% phrenic nerve block post ISB. But others (Renes et al) have evaluated it using bupivacaine and found that lower doses resulted in less diaphragm blockade. Cuvillon showed that those with a catheter had 66% phrenic nerve paralysis at 24 hours.

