## 4.0 Study Endpoints/Events/Outcomes

- 4.1 Primary Endpoint/Event/Outcome: The primary study endpoint will be diaphragm excursion (movement in cm) from rest to sigh in a sitting position.
- 4.2 Secondary Endpoint(s)/Event(s)/Outcome(s): The secondary endpoint will be the diaphragm excursion (movement in cm) from rest to a quick inspiratory breath.
- 4.3 Secondary Endpoint(s)/Event(s)/Outcome(s): Evaluation of baseline FEV1, FVC (or FEV6) and FEV1/FVC ratio via spirometry.

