## 5.0 Study Intervention(s)/Investigational Agent(s)

- 5.1 Description: This study will be run concurrently with two other studies comparing bupivacaine to Liposomal Bupivacaine in shoulder surgeries. We will either use already randomized patients for our randomization process or if they are not enrolled in either RCR or TSA study we will randomize them to one of the two groups. For this study in particular we will use an ultrasound machine to scan the diaphragm of any patient who had an Interscalene Block for Total Shoulder Arthroplasty or Rotator Cuff Repair. Patients are to be scanned in an upright sitting position and scanned from a low intercostal or subcostal approach using the liver or spleen as an acoustic window. M Mode will be applied and the range of diaphragmatic movement from the resting expiratory position to deep inspiration (sigh test) will be

recorded as was the range of diaphragmatic movement from resting expiratory position when quickly inspiring through the nose (sniff test). The blocks will be done regardless of the study as they are standard of care for pain control. The only intervention is ultrasound examination of the patient's diaphragm at baseline, 3 hours post block in recovery room and on post-operative day 1, and basic spirometry to record FEV1 and FVC via a portable spirometer at the same time points. If patients did stay in hospital on postoperative day 2 we would also evaluate their diaphragm function.

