5.2 Drug/Device Handling: n/a

5.3 Biosafety: n/a

5.4 Stem Cells: n/a

## 6.0 Procedures Involved

6.1 Study Design: This is a prospective study

Study Procedures: All patients who are enrolled in our TSA or RCR studies fit the criteria of being scheduled for overnight shoulder surgery and having an ISB with or without LB. The patients will already be randomized into either an ISB with bupivacaine or with bupivacaine and LB. If the patient is not enrolled or does not fit inclusion criteria for the RCR or TSA study they will then be randomized to either bupivacaine or liposome bupivacaine ISB. The patients will perform spirometry (one large exhale into a spirometer) and have an ultrasound examination of their diaphragm at baseline prior to the block, in PACU after their procedure, and on postoperative day 1 (24 hours after ISB). Diaphragmatic movement will be evaluated by real-time M-mode ultrasonography of the hemidiaphragm using a 17-mm 1- to 5-MHz broadband phased array US probe. Patients are to be scanned in an upright sitting position and scanned from a low intercostal or subcostal approach using the liver or spleen as an acoustic window. M Mode will be applied and the range of diaphragmatic movement from the resting expiratory position to deep inspiration (sigh test) will be recorded as well as the range of diaphragmatic movement from resting expiratory position when quickly inspiring through the nose (sniff test). This will occur three times, at baseline prior to surgery, in the recovery room, and on the ward on postoperative day 1. All nerve blocks will be confirmed to be functional via a sensory skin test prior to surgery or in the recovery room prior to the recovery room evaluation.

6.2 Study Duration: The patients will be in the study for 2 days. The duration of the study should be 3 months to enroll the 22 patients.

6.3 Individually Identifiable Health Information: PHI will be recorded but once data collection is done then the phi will be removed and replaced with unique identifier. This is just to ensure we see the correct patient for the data collection.

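### The stated 80% power is for a 24-hour block rate that is not a listed endpoint; no power or detectable difference is stated for the primary endpoint, sigh excursion in cm

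*Combined protocol and SAP*

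**What the plan says.** Section 4.1 defines the primary endpoint as a continuous measurement: "The primary study endpoint will be diaphragm excursion (movement in cm) from rest to sigh in a sitting position". It gives no time point. Sections 4.2 and 4.3 add excursion on a quick inspiration and spirometry, which are also continuous. Section 15.1 averages three ultrasound exams per time point and has the statistician "evaluate for differences (if any) between the movement of the diaphragms in each group".

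The only power statement is in 15.2. It reads "We assumed a 5% rate of block at 24 hours in bupivacaine and a 66% block for liposome bupivacaine", followed by "With an alpha of 0.05 and power of 80% we determined we need 9 patients in each group". A 20% allowance for losses raises this to 11 per group, 22 in total.

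Two other places suggest why a block rate was used. The purpose in 2.1 is "This study will evaluate if there is a possible prolonged phrenic nerve paralysis when using liposome bupivacaine", and 3.3 cites a study in which "those with a catheter had 66% phrenic nerve paralysis at 24 hours". Section 15.2 does not cite that study, so the link is inferred from the matching figure.

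On timing, 5.1 schedules ultrasound of the "diaphragm at baseline, 3 hours post block in recovery room and on post-operative day 1". Section 6.1 places the day 1 scan at 24 hours after the block. Every patient therefore has two planned post-block scans.

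**The concern.** The quantity that was powered and the quantity to be analysed are different. A block rate is a yes/no outcome, and the protocol does not say how far excursion must fall to count as a block. The planned comparison is of movement, and neither a standard deviation nor a target difference in cm is given for it.

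A reader may credit the primary comparison with 80% power that was never shown for it. If excursion does not differ significantly between groups, there is no stated target against which to read that result. Because 4.1 names no time point, it also leaves open which post-block scan carries the primary comparison.

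**Working it through.** **Inputs.** From 15.2: block rates 0.05 and 0.66, alpha 0.05, power 80%, 9 per group before and 11 after the allowance. The plan does not say whether alpha is one- or two-sided; two-sided is assumed. From 4.1: the endpoint is in cm. SD, target difference and block cut-off: none given.

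**Step 1: reproduce the plan's 9 per group.** Two proportions, pooled variance under the null, no continuity correction:

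n = [z(0.975) × √(2p̄(1−p̄)) + z(0.80) × √(p1(1−p1) + p2(1−p2))]² / (p2−p1)²

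- p̄ = (0.05 + 0.66)/2 = 0.355, so 2p̄(1−p̄) = 0.458, with square root 0.677
- p1(1−p1) + p2(1−p2) = 0.0475 + 0.2244 = 0.2719, with square root 0.521
- n = (1.960 × 0.677 + 0.842 × 0.521)² / 0.61² = 3.116 / 0.3721 = 8.37, rounded up to 9

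The stated figure reproduces for the block rate under this approximation.

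**Step 2: exact power for the block rate.** All pairs of binomial counts were enumerated, with the rates in 15.2. Maximum size is the largest type I error over all common block rates.

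| Test (two-sided 5%) | Power, 9 per group | Power, 11 per group | Maximum size at 9 |
|---|---|---|---|
| Fisher exact | 73% | 82% | 0.021 |
| Chi-square, uncorrected | 88% | 92% | 0.057 |
| Barnard unconditional exact | about 81% | not needed here | below 0.05 |

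Whether 9 per group gives 80% for a block rate, with the error rate held at 5%, depends on a test the plan does not name.

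**Step 3: detectable difference on the primary endpoint.** Two-sample t-test, two-sided 5%, n evaluable per group. The noncentrality is d × √(n/2) on 2n−2 degrees of freedom, where d is the difference in SD units.

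- n = 9: 80% power needs a noncentrality of 2.985, so d = 2.985/√4.5 = 1.41 SD
- n = 11: 80% power needs 2.945, so d = 2.945/√5.5 = 1.26 SD

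In cm, for between-patient SDs that are assumptions and not in the documents:

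| Assumed SD (cm) | 0.5 | 1.0 | 1.5 | 2.0 |
|---|---|---|---|---|
| Detectable at 9 per group (cm) | 0.70 | 1.41 | 2.11 | 2.81 |
| Detectable at 11 per group (cm) | 0.63 | 1.26 | 1.88 | 2.51 |

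**Step 4: effect of adjusting for the baseline scan.** The scan is taken, but the plan does not name it as a covariate. Adjustment multiplies the variance by (1−r²) × (1 + 1/(2n−4)), with 2n−3 degrees of freedom. The second factor is the cost of chance baseline imbalance, 1 + 1/14 = 1.071 at n = 9. For assumed baseline-to-24-hour correlations of 0.3, 0.5 and 0.7, the detectable difference at 9 per group is about 1.40, 1.27 and 1.04 SD, against 1.41 unadjusted.

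**The case against.** The best defence is that the block rate was a reasonable planning device. Section 2.1 asks about prolonged paralysis, 3.3 supplies a matching 66%, 15.2 says openly that its figure is a block rate, and the arithmetic is right under the usual approximation. All of this stands and explains the choice. It does not make the block rate an endpoint, supply a cut-off, or turn the 80% into the power of a comparison of means.

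The defence also holds in part on timing. Sections 2.1, 6.1 and 15.2 all point to 24 hours, so the intended time point is fairly clear. Section 4.1 still does not say it.

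A reader might infer that the trial is underpowered for excursion. The documents do not support that, because they give no SD or target difference. The direction is open even if 5% v 66% is taken at face value. If a block is a threshold on normally distributed excursion with equal variances, the implied shift is 1.645 + 0.412 = 2.06 SD, and the t-test has about 98% power at 9 per group. If blocked patients instead form a separate cluster 2 to 4 SD lower, simulation puts power at about 50% to 75%. Both models are assumptions.

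A reader might also infer that 9 per group is wrong, or that it secures 80% for the block rate. Neither holds: it reproduces under one approximation, and exact power varies with the test.

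**Conclusion.** The mismatch is real and should be fixed. The only stated power belongs to an outcome that is neither listed nor defined, and the primary endpoint has no stated power, detectable difference or time point. At the planned size the unadjusted detectable difference is 1.41 SD with 9 evaluable per group and 1.26 SD with 11, assuming a two-sided 5% t-test, normal data and equal variances. Any value in cm rests on an SD the sponsor has yet to state. The finding concerns what the power statement refers to. It is not a finding that 22 patients are too few.

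**What to change.** Keep the total at 22.

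1. In 4.1, name 24 hours after the block (postoperative day 1) as the primary time point, in line with 2.1, 6.1 and 15.2.
2. Make the endpoint and the power statement agree by one of two routes. Both are valid.
   - **Route A: excursion stays primary.** Say in 15.2 that the 5% v 66% calculation refers to a block rate under a normal approximation and is not the power of the primary endpoint. Add that a two-sided 5% t-test of sigh excursion at 24 hours has 80% power for a difference of 1.41 SD with 9 evaluable per group (1.26 SD with 11), converted to cm with the sponsor's stated SD assumption. If a baseline-adjusted analysis is planned, give its figure with the assumed correlation.
   - **Route B: the block rate becomes a listed endpoint.** Define it, before data are seen, as a fall from the patient's own baseline sigh excursion, with a cut-off the sponsor chooses. Name a test that holds 5% at this size and restate the power for that test; for Fisher this is 73% at 9 per group and 82% at 11. If excursion remains primary beside it, 15.2 must still say that the calculation does not refer to excursion.

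The cost is wording in 4.1 and 15.2, plus one endpoint line and its test under Route B. No extra patients, visits or measurements are needed, since sigh excursion at baseline and on day 1 is already collected. The downside is that the power statement may look less favourable. Under Route A, the detectable difference describes what a fixed sample can show and does not by itself justify that sample size.

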## 22.0 Resources Available

23.0 **Resources Available:** Research assistants are available to aid in consent and data acquisition. All research assistants will be familiar with the study protocol and have experience working with similar studies.

We plan to enroll 22 subjects. The plan is to screen 40 subjects to research this target population. This center performs approximately 500 shoulder procedures annually.

We plan to conduct this study over 3 months. Enrollment and data collection will be completed at this time. Statistical Analysis will take approximately two months to complete.

All procedures will be performed in the clinical facilities at the MHealth Clinics and Surgery Center and at the West and East Bank. Data storage and analysis will be done using desktop equipment which is available at the Research Office B573 Mayo.

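### Does the 20% loss allowance in Section 15.2 fall short because 9/0.8 rounds up to 12 per group, not 11?

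*Combined protocol and SAP*

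**What the plan says.** The sample-size reasoning is in Section 15.2 (Power Analysis). The inputs are the proportions of patients with a blocked diaphragm at 24 hours: "We assumed a 5% rate of block at 24 hours in bupivacaine" and "a 66% block for liposome bupivacaine". From these, "With an alpha of 0.05 and power of 80% we determined we need 9 patients in each group". The loss allowance follows: "Assuming we would have 20% patients drop out, screen fail, or discharge early we planned to enroll 11 per group", which makes 22 in total. Section 15.2 gives no formula for the 9, no test, no sidedness, and no rule for turning 9 into 11.

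Three other places bear on what the 20% covers. Section 11.1 plans "40 patients consented with goal of 22 patients enrolled in the study". The Resources Available section repeats the pair of numbers: "The plan is to screen 40 subjects to research this target population". Section 13.2 says how early withdrawals are recorded: "If the patient is withdrawn from study prior to the procedure, they will be noted in study records as screen failures".

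**The concern.** The standard way to protect an evaluable number against a loss fraction is to divide by the fraction retained. Applied to 9 and 20%, this gives 11.25 and hence 12. The stated 11 looks like the familiar shortcut of adding 20% to the evaluable number (9 x 1.2 = 10.8), which always gives too few. If so, the trial would miss its own evaluable target at its own loss rate, and 11 per group would absorb only 18% loss.

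In a trial of 22 patients each loss is about 9% of an arm (1/11), so a reader would reasonably check this sentence. The reader would also find that the 20% includes screen failures, although a separate allowance for patients who never enrol appears elsewhere. At stake would be power below the stated 80%, or a sample size that cannot be verified.

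**Working it through.** **Inputs.** From Section 15.2: p1 = 0.05, p2 = 0.66, alpha 0.05, power 80%, 9 per group needed, 20% loss, 11 per group enrolled. From Section 11.1: 40 consented, 22 enrolled. Assumption: alpha is two-sided, because the document does not say.

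**1. Reproduce the 9.** The pooled normal approximation for two proportions is

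n = [1.960 x sqrt(2 x pbar x (1 - pbar)) + 0.842 x sqrt(p1(1 - p1) + p2(1 - p2))]^2 / (p2 - p1)^2, with pbar = 0.355.

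The two square roots are sqrt(0.45795) = 0.677 and sqrt(0.2719) = 0.521. The bracket is 1.326 + 0.439 = 1.765, and n = 3.116/0.3721 = 8.37, rounded up to 9. This matches the plan. Other common two-sided formulas do not: unpooled 5.74 (6), arcsine 7.51 (8), continuity-corrected 11.42 (12).

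**2. Apply the 20%.**

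| Route | Result per group | Rounded up |
|---|---|---|
| 9 / 0.8 | 11.25 | 12 |
| 9 x 1.2 | 10.8 | 11 |
| 8.37 / 0.8 | 10.47 | 11 |

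The third row divides correctly by the share retained and rounds once, at the end. It gives the plan's number. The 12 arises only when 8.37 is first rounded up to 9, and the inflated 9 is then rounded up again.

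**3. Expected evaluable patients if all the loss falls within the 22.** 11 x 0.8 = 8.8 per group, and 22 x 0.8 = 17.6 in total. That is 0.4 below 18, but above the unrounded requirement of 2 x 8.37, about 16.75. The loss that still leaves 9 per group is 2/11 = 18.2%.

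**4. Power on the formula from step 1.**

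| Evaluable (bupivacaine v LB) | Power |
|---|---|
| 9 v 9 | 83.3% |
| 8.8 v 8.8 | 82.3% |
| 9 v 8 | 80.9% |
| 8 v 9 | 80.2% |
| 8 v 8 | 77.8% |
| Averaged over independent 20% loss from 11 per arm | 81.3% |

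**5. Where the losses fall.** Twenty percent of 22 is 4.4 patients, and 22 - 18 = 4 losses are already affordable. If as little as 0.4 of those 4.4 losses occurs before a patient is counted as enrolled, the shortfall is gone. Sections 11.1 and 13.2 make that plausible: 40 - 22 = 18 consented patients are expected not to be among the enrolled, and withdrawals before the procedure are recorded as screen failures.

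**The case for a change.** The strongest case for a change is that Section 15.2 says 9 are needed, not 8.37, and a plan should be held to its printed figures. By that standard the chance of success is modest. With independent 20% loss from 11 per arm, the probability of keeping at least 9 in both arms is 38%, and of keeping at least 18 of 22 overall is 54%. With 12 per arm these become 63% and 81%. The ambiguity about screen failures can also be read the other way: if they count within the 22, the shortfall stands, and the text does not say.

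The arithmetic in this is right. But 9 is a rounded threshold, and what the plan promises is 80% power. An outcome of 9 in one arm and 8 in the other counts as a miss in the 38% figure, yet still gives 80% to 81% power on the formula that yields the 9.

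That defence depends on the formula, which the plan does not name. A one-sided Fisher exact test also first passes 80% at 9 per group (81.4%, against 73.6% at 8). Weighting its exact power at each pair of retained arm sizes by the binomial(11, 0.8) probabilities gives about 78%. Nothing in Section 15.2 points to a one-sided test, and the deficit would be about two percentage points on an unsourced loss guess. With a two-sided Fisher test, power is 73.1% at 9 per group with no further loss and 73.7% averaged over 20% loss from 11, so the loss allowance is not the cause of that lower figure. The choice of test is a separate matter.

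It does stand that Section 15.2 omits the route from 9 to 11 and does not say which losses the 20% counts.

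**Conclusion.** The concern does not call for a change. As printed, 9, 20% and 11 differ from division with rounding up by one patient per group, and the expected shortfall is 0.4 of a patient in total. Inflating the unrounded requirement gives exactly 11, and on that formula the stated 80% is met: 82.3% at the expected 8.8 per group and 81.3% averaged over random loss. This rests on a two-sided alpha of 0.05, the pooled normal approximation as the source of the 9, and the worst case that all 20% is lost after enrolment. If some screen failures fall between the 40 consented and the 22 enrolled, the shortfall shrinks or disappears.

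Describing the allowance as 18%, or the evaluable number as 8.8, would correct a sentence without altering enrolment, procedures, analysis or any conclusion. Stating which losses count would add detail that the trial team can settle from its screening and enrolment records. This is rounding within a planning guess, not an underpowered design.
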